3.2. Subject Grouping

For analyses based on the FAS, subjects will be grouped according to the treatment to which they were randomized. For analyses based on the Safety Analysis Set and PK Analysis Set, subjects will be grouped according to actual treatment received. The actual treatment received will differ from the randomized treatment only when their actual treatment differs from randomized treatment for the entire treatment duration in the BD Phase.

For analyses in the BD Phase, subjects will be grouped into the following groups, and only the BD Phase data will be summarized:

- 1) BD Phase GS-9674 100 mg: This group includes all subjects who were on GS-9674 100 mg in the BD Phase;
- 2) BD Phase GS-9674 30 mg: This group includes all subjects who were on GS-9674 30 mg in the BD Phase;
- 3) BD Phase GS-9674 Pooled: This group includes all subjects who were on GS-9674 100 mg or GS-9674 30 mg in the BD Phase;
- 4) BD Phase Placebo: This group includes all subjects who were on Placebo in the BD Phase.

Treatment groups 1, 2, and 4 will be presented in efficacy tables in BD Phase. Treatment groups 1 - 4 will be presented in all tables other than efficacy tables in BD Phase.

For analyses in the OLE Phase, subjects will be grouped into the following groups, and only the OLE Phase data will be summarized:

- 5) OLE Phase GS-9674 - Previously in 100 mg: This group includes all subjects who received the OLE study drug and previously received GS-9674 100 mg in the BD Phase;
- 6) OLE Phase GS-9674 - Previously in 30 mg: This group includes all subjects who received the OLE study drug and previously received GS-9674 30 mg in the BD Phase;
- 7) OLE Phase GS-9674 - Previously in Placebo: This group includes all subjects who received the OLE study drug and previously received placebo in the BD Phase;
- 8) OLE Phase GS-9674 Total: This group includes all subjects who received the OLE study drug.

For long-term (LT) analyses, subjects will be grouped into the following groups, and data from both BD Phase and OLE Phase will be summarized:

- 9) LT GS-9674 initially in 100 mg: This group includes all subjects who received GS-9674 100 mg in the BD Phase and may or may not enter the OLE Phase;
- 10) LT GS-9674 initially in 30 mg: This group includes all subjects who received GS-9674 30 mg in the BD Phase and may or may not enter the OLE Phase.

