- In LT analysis, the ET and FU visits from BD/OLE Phase will be considered as “LTET” and “LTFU” visits. However, the LTET and LTFU visits will not be summarized in LT summary tables or figures.

3.8.3. Selection of Data in the Event of Multiple Records in an Analysis Visit Window

Depending on the statistical analysis method, single values may be required for each analysis window. For example, change from baseline by visit usually requires a single value, whereas a time-to-event analysis would not require 1 value per analysis window.

If multiple valid, nonmissing, continuous measurements exist in an analysis window, records will be chosen based on the following rules if a single value is needed:

- In general, the baseline value will be the last nonmissing value on or prior to the first dosing date of study drug in the corresponding study phase, unless specified differently. If multiple measurements occur on the same day, the last nonmissing value prior to the time of first dosing of study drug will be considered as the baseline value. If these multiple measurements occur at the same time or the time is not available, the average of these measurements (for continuous data) will be considered the baseline value.
- Baseline values of the liver tests (ALP, ALT, AST, and total bilirubin) in the BD Phase will be determined by averaging the values obtained at Screening and Baseline/Day 1. For the calculated baseline values, the reference range for each parameter will be defined as the one associated with the latest visit among all the values being averaged for each subject, for the purpose of determination of the abnormality and/or toxicity grades.
- For postbaseline values:
 - The record closest to the nominal day for that visit will be selected.
 - If there are 2 records that are equidistant from the nominal day, the later record will be selected.
 - If there is more than 1 record on the selected day, the average will be taken, unless otherwise specified.

If multiple valid, nonmissing, categorical measurements exist in an analysis window, records will be chosen based on the following rules if a single value is needed:

- For baseline, the last available record on or prior to the date of the first dose of study drug will be selected. If there are multiple records with the same time or no time recorded on the same day, the value with the lowest severity will be selected (eg, normal will be selected over abnormal for safety ECG findings).

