7.6. Other Safety Measures

7.6.1. Partial Mayo Score

The partial Mayo score is a survey score for the assessment of IBD that considers stool frequency and rectal bleeding. At each study visit, two sub score components will be reported:

- Stool frequency sub score: a numeric value ranging from 0 to 3 (where 0 = normal for the patient, 1 = 1 – 2 stools more than normal, 2 = 3 – 4 stools more than normal, 3 = 5 or more stools more than normal);
- Rectal bleeding sub score: a numeric value ranging from 0 to 3 (where 0 = no blood seen, 1 = streaks of blood with stool less than half the time, 2 = obvious blood with stool most of the time, 3 = blood alone passes).

Partial Mayo score will be calculated as the sum of the above two sub scores. If one or both sub scores are missing, partial Mayo score will be considered missing.

Partial Mayo score and its two components will be reported for subjects with IBD history based on the Safety Analysis Set for the BD Phase, and the LT analysis. Partial Mayo score in the OLE Phase will be summarized based on the OLE Analysis Set.

Descriptive statistics will be provided for partial Mayo score in the BD Phase, the OLE Phase and the LT analysis according to treatment groups in Section [3.2](#) as follows:

- Baseline value
- Values at each postbaseline visit
- Change from baseline at each postbaseline visit

A baseline value will be defined as the last available value collected on or prior to the date/time of first dose of study drug in the BD Phase. Change from baseline to a postbaseline visit will be defined as the postbaseline value minus the baseline value. Partial Mayo scores calculated at unscheduled visits will be included for the baseline value selection.

For each subject, the nadir will be determined as the minimum score from baseline to the last available visit; change from nadir will be calculated only for visits that are after the earliest visit with the nadir value. Nadir values will be summarized using descriptive statistics.

Subjects with change from nadir at any visit \geq 2 points and within 30 days of the last dose in each phase will be identified. Number and percent of these subjects will be reported. Maximum change from nadir for these subjects will be summarized.

In the case of multiple values in an analysis window, data will be selected for analysis as described in Section [3.8.3](#). No formal statistical testing is planned.

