A by-subject listing of available partial Mayo scores, its two components, nadir and change from nadir will be provided by subject ID number and visit in chronological order. Any subject with a history of IBD who experiences at least a 2-point increase from nadir in the partial Mayo score during the course of the study within 30 days of the last dose will be flagged in the listing.

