a The visit window may be extended under special circumstances with explicit approval of the Medical Monitor. Subjects who fail to meet eligibility criteria due to an abnormal laboratory result may undergo re-testing of the abnormal analyte during the screening window. This will be done at the discretion of the investigator and also with prior approval of the Medical Monitor.

b Blinded Study Phase subjects discontinuing the study at any time for any reason (Early Termination – ET) should complete the procedures listed for the Week 12/ Visit AND the follow-up visit. OLE Phase subjects discontinuing the study at any time for any reason (Early Termination – ET) should complete the procedures listed for the Week 96/ Visit AND the follow-up visit if possible.

c After completing 12 weeks of treatment in the Blinded Study Phase, subjects will return for the follow-up visit 4 weeks post the last dose of the study drug and at that time they can begin their OLE Phase. Follow-up visit for Blinded Study Phase and Baseline/Day 1 OLE visit can occur on the same day if convenient. If OLE Baseline/Day 1 and Blinded study follow-Up visit is on the same day subjects should only complete OLE Baseline/Day 1 assessments.

d Follow-up visit should be completed during the Blinded Study Phase as well as the OLE Phase.

e Obtain written informed consent before initiation of any screening procedure.

- f Phone follow-up every 4 weeks after OLE Week 12, (OLE Week 16, 20, 28, 32, 40, 44, 52, 56, 64, 68, 76, 80, 88 and 92).
- g QoL questionnaires and Pruritus assessments should be completed prior to any study procedures being performed and prior to the subject seeing a health care provider. Refer to the Study Reference Binder for guidance on QoL questionnaire administration. During OLE, QoL questionnaires are required at OLE Baseline/Day 1, Weeks 4, 12 and every 12 weeks thereafter.
- h Complete PE at screening and symptom-directed PE for other visits. The focus of a symptom-driven physical examination will be determined by the investigator based on subject complaint.
- i Vital signs include (heart rate, systolic and diastolic blood pressure, respiratory rate, and body temperature)
- j Height should be collected at Screening and Baseline/Day 1 only. Weight should be collected at all visits. Refer to the Study Reference Binder for specific instructions on how weight should be measured.

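### The partial Mayo nadir can be set by a later visit, so a rise of 2 or more points before a strictly new low gets no change value and can be missed by the count and the flag

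*SAP*

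**What the plan says.** SAP section 7.6.1 (Partial Mayo Score) sums two sub scores of 0 to 3 each, so the total runs from 0 to 6. For every subject "the nadir will be determined as the minimum score from baseline to the last available visit", and "change from nadir will be calculated only for visits that are after the earliest visit with the nadir value".

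Three outputs rest on that quantity:

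- the number and percentage of subjects with a change from nadir of at least 2 points, where those "within 30 days of the last dose in each phase will be identified";
- the maximum change from nadir among these subjects;
- a flag for subjects with IBD history whose rise of at least 2 points occurs "during the course of the study within 30 days of the last dose will be flagged in the listing".

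The baseline is "the last available value collected on or prior to the date/time of first dose of study drug in the BD Phase". Section 3.2 says that for OLE Phase analyses "only the OLE Phase data will be summarized". Section 3.8.2 says that "the LTET and LTFU visits will not be summarized in LT summary tables or figures". Footnote c of the Study Procedures Table (Appendix 1) says that "subjects will return for the follow-up visit 4 weeks post the last dose of the study drug", and the column heading allows 5 days either side.

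**The concern.** A nadir is meant to be the best state reached before the worsening being judged. Here the minimum is taken over all visits, including those after the worsening. If the subject later reaches a new low, that later visit becomes the nadir and every earlier visit, including the flare, has no change value. Of two subjects with the same flare, the one who later improves further is the one removed.

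The primary objective is safety and tolerability, and this is the SAP's subject-level threshold count and flag for IBD worsening. The planned groups are 20, 20 and 10. One missed subject is 1/20 = 5 or 1/10 = 10 percentage points of a full group, and more when the denominator is only subjects with IBD history.

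A second, smaller point is that the section does not fix the period over which the nadir runs for the OLE table, the LT analysis or the single listing flag.

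**Working it through.** **Rules compared.** Let S(t) be the score at visit t.

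- As written: N = minimum of S over all visits, and t* = earliest visit with S = N. The change is S(t) − N for t after t* only.
- Running nadir: the change is S(t) − (minimum of S over visits before t), for every postbaseline t.

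**Direction of error.** After t* the running nadir equals N, so the two rules agree there. Before t* only the running nadir yields values. With the phase scope fixed, the written rule can therefore never count a subject that the running nadir does not.

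**When a subject is missed.** Suppose the score rises from a low L to a peak P ≥ L + 2 and later falls to N < L. Since N ≥ 0, L is at least 1, P is at least 3, and the fall P − N is at least 3. The subject is missed if no rise of 2 or more points follows t*. Subjects with baseline 0, or who only return to their earlier low, are not affected.

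**Worked cases** (Baseline, Weeks 1, 2, 4, 8, 12, BD follow-up):

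| Scores | Maximum change as written | Maximum change, running nadir |
|---|---|---|
| 1,1,3,3,1,0,0 | 0 (only the follow-up has a value: 0 − 0) | 3 − 1 = 2 |
| 3,1,3,1,0,0,0 | 0 (Week 12 and follow-up: 0 − 0) | 3 − 1 = 2 |
| 1,1,3,3,1,1,1 | 3 − 1 = 2 | 2 |
| 2,5,1,1,3,1,1 | 3 − 1 = 2 | 5 − 2 = 3 |

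The third row shows that a tie with the earlier low does no harm. The fourth shows a subject who is still counted, but with the maximum change understated.

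**Complete check of the logic.** Over all 7^7 = 823,543 possible sequences of seven scores, the written rule never adds a subject, and the four conditions above pick out the missed sequences with no exception in either direction. With scores limited to 0–2, 0 of the 1,611 sequences with a rise of 2 or more points are missed. These are counts of patterns, not expected frequencies.

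**Phase scope.** The BD table uses BD data only (section 3.2). Three outputs stay open.

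- *OLE table.* Section 7.6.1 starts at the BD baseline, while section 3.2 restricts OLE summaries to OLE data. With BD all 0 and OLE all 2, the OLE change is 2 − 0 = 2 if the nadir spans phases (counted) and 2 − 2 = 0 if it restarts (not counted).
- *LT analysis.* Take BD scores 1,1,1,1,3,1 (Baseline to Week 12), then 1 through OLE Week 24 and 0 afterwards. The BD table gives 3 − 1 = 2. The LT analysis gives 0 as written if the nadir spans phases, and 2 with a running nadir. Nothing says whether a follow-up score, which is kept out of LT tables, can set the LT nadir.
- *Listing flag.* The flagged rise must lie within 30 days of the last dose, but the nadir has no such limit. BD follow-up falls at 28 ± 5 days, that is days 23 to 33, so a score taken on days 31 to 33 is too late to be flagged but can still set the nadir. With BD visits all 1, a late follow-up of 0 and OLE all 2, an across-phase running nadir gives 2 − 0 = 2 if that follow-up score counts and 2 − 1 = 1 if it does not. This cannot happen when follow-up and OLE Day 1 coincide, because then only the OLE Day 1 assessments are done.

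**The case against.** The strongest reply is that this matters little. A miss needs four conditions together, and every missed subject later scores below all pre-rise values, baseline included. The output is descriptive, in about 50 subjects, and restricted to those with IBD history. The listing shows every score with its components, and adverse event tables and by-visit change from baseline are reported separately. All of that is true and is why the reach is called modest. It does not rescue the rule, because none of those outputs gives a threshold count. In 3,1,3,1,0,0,0 the changes from baseline are −2, 0, −2, −3, −3, −3, so only the raw scores show the rise. It is fair to add that this subject never exceeds baseline, so the case carries less clinical weight than the first.

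On scope, one can argue that section 7.6.1 implies a single nadir per subject from the BD baseline. It anchors the baseline to the BD Phase, whereas section 7.3 on vital signs uses the reporting phase, and section 3.2 may govern only which visits are tabulated. That is a plausible reading, but the SAP does not state it, and two programmers could report different OLE counts. The late follow-up case is narrow, and in the example counting that score raises the OLE change. It is a clarification, separate from the under-count.

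**Conclusion.** The concern holds. Applied as written, the rule can omit subjects who had a rise of 2 or more points, or understate their maximum change. For a fixed phase scope it never errs the other way. The individual effect is shown by the worked cases (0 against 2). The number of subjects affected cannot be derived from the SAP, and no prevalence is claimed. The defect should be fixed because it bears on a safety threshold measure and costs little to correct. The conclusion rests on reading the nadir as the literal minimum over all visits in the analysis period. The open phase scope is a secondary gap.

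**What to change.** Replace the nadir sentence in section 7.6.1 with:

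> At each postbaseline visit the nadir is the lowest score from baseline up to the preceding visit (running nadir). Change from nadir is the score at that visit minus the running nadir.

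Use it for the count of subjects with a change of 2 or more points, the maximum-change summary and the listing flag. The descriptive summary of nadir values can stay as the lowest score in the stated period.

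Also state:

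- for the OLE table, the LT analysis and the listing flag, whether the nadir restarts in each phase and which baseline starts it;
- if it spans phases, whether a BD follow-up score taken more than 30 days after the last BD dose can set the nadir for OLE visits, since the running nadir removes the 30-day mismatch only within a phase;
- whether unscheduled scores can set the nadir, because section 7.6.1 mentions them only for baseline selection.

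The cost is SAP wording and minor programming, with no new data. With the phase scope held fixed, counts stay the same or rise. Moving from an across-phase to a within-phase nadir can lower the OLE count, as in the case of BD all 0 and OLE all 2.

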3.8.2. Analysis Visit Windows

Subject visits might not occur on protocol-specified days. Therefore, for the purpose of analysis, observations will be assigned to analysis windows.

The analysis windows to be applied to the BD Phase are provided in [Table 3-1](#), [Table 3-2](#), [Table 3-3](#) and [Table 3-4](#), except that the algorithm for assigning baseline analysis window does not apply to the liver tests (ALP, ALT, AST, and total bilirubin). For these 4 parameters, the baseline values will be determined by averaging the values obtained at screening and Baseline/Day 1, and no specific study day is associated with the average values.

Table 3-1. Analysis Visit Windows in BD Phase for Partial Mayo Score, Vital Signs, Body Weight, Pruritus Measures, Chemistry, Hematology, Coagulation Laboratory, and Mayo Risk Score

Analysis Visit	Study Day	Lower Limit	Upper Limit
Baseline	1	NA	1
Week 1	8	2	11
Week 2	15	12	21
Week 4	29	22	42
Week 8	57	43	70
Week 12	85	71	≥ 85

NA = not applicable

Table 3-2. Analysis Visit Windows in BD Phase for Lipid Profiles and Pooled Cohort Risk Score

Analysis Visit	Study Day	Lower Limit	Upper Limit
Baseline	1	NA	1
Week 1	8	2	18
Week 4	29	19	42
Week 8	57	43	70
Week 12	85	71	≥ 85

NA = not applicable

Table 3-3. Analysis Visit Windows in BD Phase for Fibroscan®, QoL Questionnaires, and Electrocardiogram (ECG), HOMA-IR, HbA1c, C-peptide, Insulin, ELF™ Score, FibroSURE/FibroTest, High-sensitivity C-reactive Protein (hsCRP)

Analysis Visit	Study Day	Lower Limit	Upper Limit
Baseline	1	NA	1
Week 12	85	2	≥ 85

NA = not applicable

Table 3-4. Analysis Visit Windows in BD Phase for FGF19, C4 and Total Bile Acids

Analysis Visit	Study Day	Lower Limit	Upper Limit
Baseline	1	NA	1
Week 1	8	2	18
Week 4	29	19	56
Week 12	85	57	≥ 85

NA = not applicable

The analysis windows to be applied to the OLE Phases are provided in [Table 3-5](#), [Table 3-6](#), [Table 3-7](#), [Table 3-8](#), [Table 3-9](#) and [Table 3-10](#).

Table 3-5. **Analysis Visit Windows in OLE Phase for Partial Mayo Score, Vital Signs, Body Weight, Lipid Profiles, Pruritus Measures, Chemistry, Hematology, Coagulation Laboratory, Pooled Cohort Risk Score and Mayo Risk Score**

Analysis Visit	OLE Study Day	Lower Limit	Upper Limit
OLE Baseline	1	NA	1
OLE Week 1	8	2	11
OLE Week 2	15	12	21
OLE Week 4	29	22	42
OLE Week 8	57	43	70
OLE Week 12	85	71	126
OLE Week 24	169	127	210
OLE Week 36	253	211	294
OLE Week 48	337	295	378
OLE Week 60	421	379	462
OLE Week 72	505	463	546

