In LT analysis, the above endpoints (except for Pooled Cohort Risk Score and Mayo Risk Score) will first be mapped to visit windows in the BD Phase and the OLE Phase (if applicable), respectively. The LT analysis window will be mapped from their BD Phase window and OLE Phase window:

- The baseline visit of BD Phase is to be mapped to LT Baseline
- The on-treatment visits of BD Phase are to be mapped to the same Week number in LT analysis, ie, Week 1, 2, 4, 8, 12 will be mapped to LT Week 1, 2, 4, 8, 12 accordingly
- The baseline visit of OLE Phase is to be mapped to LT OLE Baseline
- For visits in OLE phase, the on-treatment analysis visits will be mapped to 12 weeks after their originally assigned OLE week numbers, eg, data from OLE Week 1, 2, 4 will be mapped as LT Week 13, 14, 16 accordingly.

The mapping algorithm is provided in [Table 3-11](#).

Table 3-11. Mapping Algorithm from Visit Windows from BD/OLE Phase to LT Analysis

BD/OLE Analysis Visit	LT Analysis Visit	Study Day
Baseline	LT Baseline	1
Week 1	LT Week 1	8
Week 2	LT Week 2	15
Week 4	LT Week 4	29
Week 8	LT Week 8	57
Week 12	LT Week 12	85
OLE Baseline	LT OLE Baseline	85
(OLE Week 1)	(LT Week 13)	92
(OLE Week 2)	(LT Week 14)	99
OLE Week 4	LT Week 16	113
OLE Week 8	LT Week 20	141
OLE Week 12	LT Week 24	169
OLE Week 24	LT Week 36	253
OLE Week 36	LT Week 48	337
OLE Week 48	LT Week 60	421
OLE Week 60	LT Week 72	505
OLE Week 72	LT Week 84	589
OLE Week 84	LT Week 96	673
OLE Week 96	LT Week 108	757

Note: Only map applicable visits per endpoint. LT OLE Baseline visit is not an on-treatment visit, which is included in the LT summary for reference, and carried the target study day as LT Week 12. Summary statistics from LT Week 13 and 14 will not be included in the tables and figures of LT analysis.

Data relating to unscheduled visits may be assigned to a particular visit or time point. The following conventions will be followed:

- An unscheduled visit prior to the first dosing of study drug may be included in the calculation of the baseline value, if applicable.
- Unscheduled visits after the first dose of study drug will be included in determining the maximum postbaseline toxicity grade.
- For subjects who prematurely discontinue from the study, ET data will be summarized as a separate visit, labeled as “Early Termination Visit” of each phase.
- Data collected on a follow-up visit will be summarized as a separate visit and labeled “Follow-up Visit” of each phase.

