Appendix 1. Study Procedures Table

		Blinded Study Phase Treatment Weeks (± 3 days)							OLE Weeks (± 3 days weeks 1-12 and ± 5 days weeks 24-96)		
		Screening ^a	Baseline (Day 1)	Week 1	Week 2	Week 4	Week 8	Week 12 /ET ^b	Blinded Study Phase follow-up visit ^c (± 5 days)	OLE Baseline/Day 1, Weeks 1, 2, 4, 8, 12, 24, 36, 48, 60, 72, 84, 96/ET ^b	OLE follow-up ^d
Subject Fasting		X	X	X	X	X	X			X	
Written Informed Consent ^e	X										
Review Inclusion/Exclusion Criteria	X	X									
Medical History	X										
Partial Mayo Score ^f	X	X	X	X	X	X	X	X	X	X	
Pruritus VAS &5D-Itch ^g		X	X	X	X	X	X	X	X	X	
QoL SF-36, PSC-PRO & PBC-40 ^g		X					X	X	X		
Symptom-directed PE ^h	X	X	X	X	X	X	X	X	X	X	
Vital Signs ⁱ	X	X	X	X	X	X	X	X	X	X	
Height and weight ^j	X	X	X	X	X	X	X	X	X	X	
Chemistry	X	X	X	X	X	X	X	X	X	X	
Hematology	X	X	X	X	X	X	X	X	X	X	
Coagulation Panel	X	X	X	X	X	X	X	X	X	X	

		Blinded Study Phase Treatment Weeks (± 3 days)							OLE Weeks (± 3 days weeks 1-12 and ± 5 days weeks 24-96)	
		Screening ^a	Baseline (Day 1)	Week 1	Week 2	Week 4	Week 8	Week 12 /ET ^b	Blinded Study Phase follow-up visit ^c (± 5 days)	OLE Baseline/Day 1, Weeks 1, 2, 4, 8, 12, 24, 36, 48, 60, 72, 84, 96/ET ^b
Cirrhosis Assessments	X									
Lipid Profile		X	X		X	X	X	X	X	X
C-Peptide, Hemoglobin A1C and Insulin		X					X			
Blood Biomarkers ^k for Biomarkers ^k	X	X	X		X		X	X	X	
Single PK and PD Sampling		X ¹	X	X	X	X	X			
HIV-1, HBV and HCV Serology	X									
Pregnancy Test ^m	X	X	X		X	X	X	X	X	X
Serum FSH ⁿ	X									
PPD										
12- lead ECGs		X					X			
Fibroscan ^p		X					X			
MRE ^q		X							X	
MRCP ^r		X							X	

		Blinded Study Phase Treatment Weeks (± 3 days)							OLE Weeks (± 3 days weeks 1-12 and ± 5 days weeks 24-96)	
		Screening ^a	Baseline (Day 1)	Week 1	Week 2	Week 4	Week 8	Week 12 /ET ^b	Blinded Study Phase follow-up visit ^c (± 5 days)	OLE Baseline/Day 1, Weeks 1, 2, 4, 8, 12, 24, 36, 48, 60, 72, 84, 96/ET ^b
Urine drug screening	X									
Urine collection (Biomarkers) ^e		X	X		X		X	X	X	
Stool collection (Biomarkers) ^e		X					X	X	X	
PPD										
Dispense GS-9674/PTM GS-9674 ^v		X			X	X			X	
Concomitant Medications	X	X	X	X	X	X	X	X	X	X
Adverse Events	X	X	X	X	X	X	X	X	X	X
Take GS-9674/PTM GS-9674 Tablets		X – Daily (Baseline/ Day 1 to Week 12) ^w							X-Daily (OLE Baseline/ Day 1 to Week 96)	

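### SAP 7.6.1 does not say whether the partial Mayo nadir and ≥2-point count use the 4-weekly OLE phone scores; read naturally, only the clinic score in each window counts

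*SAP*

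**What the plan says.** **Schedule.** In the SAP's Appendix 1 procedures table the row "Partial Mayo Score ^f" carries footnote f, which reads "Phone follow-up every 4 weeks after OLE Week 12, (OLE Week 16, 20, 28, 32, 40, 44, 52, 56, 64, 68, 76" and continues with Weeks 80, 88 and 92. That makes 14 contacts. Clinic visits after OLE Week 12 are 12 weeks apart, and the column heading gives their tolerance: "OLE Weeks (± 3 days weeks 1-12 and ± 5 days weeks 24-96".

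**Windows.** Table 3-5 ("Analysis Visit Windows in OLE Phase for Partial Mayo Score, Vital Signs, Body Weight, Lipid Profiles, Pruritus Measures" and other measures) has these analysis visits after OLE Week 12: Weeks 24, 36, 48, 60, 72, 84 and 96. Section 3.8.2 maps on-phase data for the listed endpoints to these windows unless the nominal visit is early termination or follow-up.

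**Selection.** For postbaseline values Section 3.8.3 says "The record closest to the nominal day for that visit will be selected". The rule operates where the analysis needs one value per window.

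**Partial Mayo analysis.** Section 7.6.1 takes the nadir as the lowest score from baseline to the last available visit. It computes change from nadir only for visits after the first one at which the nadir occurs. It then counts subjects whose change reaches 2 points at any visit within 30 days of last dose in the phase, and summarises the maximum change. The next paragraph begins "In the case of multiple values in an analysis window, data will be selected for analysis as described in Section" and points to 3.8.3. A by-subject listing of available scores flags rises of at least 2 points.

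**The concern.** The rise of at least 2 points from nadir is the SAP's own summary of IBD worsening over 96 weeks of open-label treatment. Scores every 4 weeks can show a rise that has settled by the next 12-weekly clinic visit, but only if they enter the calculation. Section 7.6.1 does not say that they do, and its reference to 3.8.3 suggests that they do not.

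Two programmers could both follow the text and report different numbers of subjects with worsening. The table (possibly windowed scores) and the listing (available scores) could also disagree within one study report, with no rule saying which stands.

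**Working it through.** The plan gives no figure to reproduce. The check places each phone contact in its window and applies the selection rule.

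**1. Does the footnote belong to this row?** The letters run in order down the table: e on informed consent, f on Partial Mayo, g on the pruritus and QoL rows. So f is attached to Partial Mayo. Its text does not say that the score is taken by phone; that is inferred from its position.

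**2. Where do the phone contacts fall?** Target day = 7 × week + 1, as in Table 3-5 (Week 24 = Day 169).

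| OLE window (days) | Nominal day | Phone weeks (target day) |
|---|---|---|
| Week 12 (71–126) | 85 | 16 (113) |
| Week 24 (127–210) | 169 | 20 (141), 28 (197) |
| Week 36 (211–294) | 253 | 32 (225), 40 (281) |
| Week 48 (295–378) | 337 | 44 (309), 52 (365) |
| Week 60 (379–462) | 421 | 56 (393), 64 (449) |
| Week 72 (463–546) | 505 | 68 (477), 76 (533) |
| Week 84 (547–630) | 589 | 80 (561), 88 (617) |
| Week 96 (631 on) | 673 | 92 (645) |

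All 14 fall in a clinic visit's window, each 28 days from the nominal day (for example 197 − 169 = 28).

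**3. Which record is selected?** A clinic visit within tolerance is at most 3 days (Week 12) or 5 days (Week 24 onward) from nominal. No phone tolerance is stated. With ±5 days assumed, a phone record is 23 to 33 days away, so the clinic record is selected whenever it is present.

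**4. How many scores are left out on this reading?** After OLE Week 12 there are 7 clinic + 14 phone = 21 scheduled scores, and 14/21 = 67%. From OLE Week 1 there are 12 clinic + 14 phone = 26, and 14/26 = 54%.

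**5. What could that mean for detection?** The documents give no episode length, so this is an illustration. Assume an episode of L days that starts uniformly from Day 86, ends by Day 673, and no missed contacts. There are 673 − L + 1 − 85 possible start days. Count those for which the episode covers a contact's target day.

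| L (days) | Clinic days only | Clinic and phone |
|---|---|---|
| 14 | (6×14 + 1)/575 = 15% | (20×14 + 1)/575 = 49% |
| 28 | (6×28 + 1)/561 = 30% | (20×28 + 1)/561 = 100% |
| 56 | (6×56 + 1)/533 = 63% | 100% |
| 84 | 100% | 100% |

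The loss matters for short episodes and disappears at 12 weeks.

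**6. Is the direction of the count fixed?** No, because the nadir is taken over the whole follow-up and only later visits are compared with it.
- *Phone scores add a case:* every clinic score is 1 and the Week 28 phone score is 4. Clinic scores alone show no rise; with phone scores the rise is 3.
- *Phone scores remove a case:* baseline 1, Week 24 = 4, all other clinic scores 1. Clinic scores alone put the nadir at baseline, and the Week 24 rise is 3. Add a phone score of 0 at Week 92: the nadir moves to Week 92, only Week 96 is compared with it (1 − 0 = 1), and the subject is no longer counted.

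**The case against.** The strongest reply is that 3.8.3 is conditional. It selects a record only where the method needs one value per window, and its example of such a need is change from baseline by visit. A minimum over time and a count over any visit need no such value. The same cross-reference appears in Sections 7.2.1 and 7.3, where it serves by-visit summaries, and 7.6.1 contains such a summary too. This stands to the extent that an all-scores reading is possible, so a reader should not conclude that the plan definitely discards the phone scores.

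The wider text still leans the other way. Section 7.6.1 works visit by visit, puts the cross-reference directly after the nadir and count paragraphs, and admits unscheduled scores only for choosing the baseline. Where the SAP wants every record it says so: Section 3.8.2 states "Unscheduled visits after the first dose of study drug will be included in determining the maximum postbaseline toxicity grade", Section 7.2.2 takes laboratory abnormalities at any postbaseline time point, and Section 7.2.3 takes all postbaseline visits.

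Other replies also stand in part:
- The listing covers available scores and flags rises during the study, so a rise seen by phone need not vanish from all output. A listing does not replace the count or the maximum-change summary.
- If the clinic score is missing, a phone score is selected, so the loss is not absolute.
- A reader might infer that worsening is necessarily under-reported. Step 6 of the working shows that the SAP's nadir definition does not support this.

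**Conclusion.** The point holds as an unresolved rule whose more natural reading leaves out scheduled safety data. On that reading, up to 14 of the 21 scheduled partial Mayo scores after OLE Week 12 do not enter the nadir, change from nadir, maximum change or ≥2-point count. A rise seen only by phone is then uncounted in the table, and the table can disagree with the listing flag.

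This assumes that the phone contact records the score and that the clinic score is present in its window. The 67% is a share of scheduled scores, not of missed events, and the detection percentages depend on an assumed episode length.

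The scope is limited to descriptive OLE and long-term summaries in subjects with IBD history. Because safety is the primary objective, a reader might infer that the primary analysis is compromised. It is not: that analysis covers the blinded phase, which has no phone contacts.

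**What to change.** In 7.6.1, state that:
- the nadir, change from nadir, ≥2-point count, maximum change and listing flag use all non-missing partial Mayo scores in date order, phone and unscheduled contacts included, within the 30-day limit already stated;
- each score is compared with the lowest earlier score, so that a later low cannot erase an earlier rise;
- 3.8.3 selection applies only to the by-visit descriptive summaries.

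The second item is needed for the first to be a clear gain. With a comparison against the lowest earlier score, an added record can lower the reference for later scores or add a new rise, but it cannot remove a subject already counted. In the example above, the Week 24 rise of 3 stays counted whatever is recorded at Week 92.

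The cost is a short SAP amendment and a programming change on contacts already scheduled. Phone and clinic scores would be mixed, which the listing can show by contact type, and the count may rise. If the comparison rule is written for all phases it also applies to the blinded-phase count, where on the same scores it can only leave the count unchanged or raise it. If the SAP is already final, its Introduction requires the change to be documented in the study report.
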